8.3. Analysis Populations

Statistical analysis will be done on the following populations:

- Intent to Treat (ITT) Population: The ITT Population will include all patients who were randomized.
- Safety Population: The Safety Population will include all patients who were treated with at least one dose of the study drug. Patients will be analyzed according to the actual treatment they receive.
- PK Population: The PK Population will include all patients who were treated with at least one dose of the study drug and have at least one usable PK measurement.

8.4. Statistical Analyses

The results of this study will be reported using summary tables, listings, and figures (TLFs), as appropriate. Continuous variables will be summarized using descriptive statistics (sample size [n], mean, standard deviation [SD], coefficient of variation [CV%; as appropriate], median, minimum, maximum, and geometric mean and geometric CV% [as appropriate for PK parameters]). Categorical variables will be summarized by presenting the number (frequency) and percentage in each category. Differences between treatment groups will be assessed by ANCOVA for continuous variables and a chi-square test for categorical variables. Pearson's correlation will be used to quantify the relationship between covariates of interest, and logistic regression may be used to simultaneously assess the relationship of multiple variables on treatment response (if enrollment provides sufficient sample size). Time to Relapse will be described with Kaplan-Meier Curves and treatment groups compared with a log-rank test.

8.4.1. Study Patients and Demographics

8.4.1.1. Disposition and Withdrawals

The numbers of patients randomized, completing, and withdrawing, along with reasons for withdrawal, will be tabulated overall and by treatment group. The number of patients in each analysis population will be reported.

8.4.1.2. Protocol Deviations

Protocol deviations will be identified and listed.

8.4.1.3. Demographics and Other Baseline Characteristics

These analyses will be conducted for the safety populations.

Demographic and baseline characteristics (including sex, age, gender, ethnicity, race, height/length, and weight) will be summarized by descriptive statistics. No formal statistical analyses will be performed. Medical history and clinical laboratory test results will be listed.

Prior and concomitant medications will be summarized by the number and percentage of patients taking each medication. They will also be classified by using the World Health Organization Drug Dictionary Anatomical Therapeutic Chemical classes and preferred terms.

8.4.2. Exposure and Compliance

The exposure to study medication will be summarized by descriptive statistics.

8.4.3. Efficacy Analyses

A 9-hour video EEG will be conducted during the Screening Period (Baseline) and a 24-hour video EEG will be conducted from Day 14 to Day 15 of the Initial Treatment Period. In addition, to confirm parent/caregiver report of relapse or complete resolution a 9-hour video EEG will be conducted during the Extended Treatment Period. For each video EEG, the number of spasms will be counted and the presence of hypsarrhythmia determined. Change from Baseline for each measure will be summarized by the median difference. Patients will be defined as having Complete Response, Partial Response, or Non-Response on Day 15 as defined in [Table 2](#), the percentage of patients who achieve a Complete Response and Partial Responders in each treatment arm will be compared using a chi-square test.

The results of the CGI-I assessments will be listed and summarized by descriptive statistics as appropriate. The responses to the seizure diary will also be summarized by dose level and scheduled time point. All efficacy summaries will be based on the ITT Population.

Details of these summaries will be provided in the SAP. For all inferential statistical tests, a 2-sided type I error rate of 0.05 will be used throughout.

For the secondary efficacy endpoints, to maintain the trial-wise type I error rate at 0.05, a fixed sequence multiple comparisons correction with fallback will be used. The assignment of alpha levels to hypotheses being tested will be specified in the SAP.

For endpoints that are continuous in nature number, the number of observations, mean, median, minimum and maximum, and standard deviation (SD) values will be presented as descriptive statistics. For inferential statistics:

- If the normality assumption is met, analysis of covariance (ANCOVA) using the baseline value as a covariate will be used.
- If the normality assumption is not met, a rank-ANCOVA analysis i.e., an ANCOVA analysis on rank-transformed data or other non-parametric methods will be used.
- Time to event analyses will be described with Kaplan-Meier curves and treatment groups compared with log-rank tests.

For endpoints that are categorical in nature, frequency, counts, and percentages will be presented as descriptive statistics, and a chi-square test will be used for inferential statistics.

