Patients will have a, minimum of a 9-hour video EEG that includes at least one full sleep-wake cycle during their Screening Visit to establish their baseline level of infantile spasms and hypsarrythmia and a 24-hour video EEG at Visit 5 (Day 14 to Day 15) of the Initial Treatment Period to establish their final level of infantile spasms and hypsarrythmia. A blinded central reader, not involved in the study, will evaluate the video EEGs and determine responder status. Details of the video EEG assessment will be provided in the video-EEG Charter. The treatment response categories are summarized in [Table 2](#). In addition, a 9-hour video EEG will be conducted during the Extended Treatment Period to confirm parent/caregiver report of relapse. If possible, a 9-hour video EEG will be conducted for patients who have continued into the Extended Treatment Period and decided to Early Withdraw. A video EEG is not required for patients who decide to withdraw during the Initial Treatment Period.

Table 2: Video EEG Response Definitions

Response Category	Definition
Complete Response	Complete resolution of spasms and hypsarrythmia confirmed by video EEG
Partial Response	Complete resolution of either spasms or hypsarrythmia confirmed by video EEG
Non-Response	No improvement or worsening of spasms/hypsarrythmia burden

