### **5.2. Efficacy Assessments**

#### **5.2.1. Video-EEG**

Video-EEGs performed during the Screening Visit and Visit 4 to Visit 5 (Day 13 and Day 14), and during the Extended Treatment Period to confirm parent reports of relapse or seizure cessation. Data collected include: *Presence of spasms (Y/N), Number of spasms, and presence of Hypsarrhythmia (Y/N), presence of epileptic encephalopathy (Y/N).*

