## 14.2. Sample Table of Contents for Data Display Summaries

Title		Population	Comments
Study Population Section			
9.1.1	Summary of Subject Disposition	Randomized	Unique
7.4.1	Summary of Analysis Populations	Randomized	Unique
10.1.1	Summary of Demographic Characteristics	Safety	Unique
10.1.2	Summary of Demographic Characteristics	ITT	Repeat 9.3.1
Efficacy Section			
Figures			
11.7.1	Correlation between trough plasma drug levels and response	ITT	Unique
11.6.2		ITT	Unique
Tables			
11.6.1	Summary of Complete Responders	ITT	Unique
11.7.1	Summary of Partial Response – absence of spasms	ITT	Unique
11.7.2	Summary of Partial Response – absence of hypersarrhythmia	ITT	
11.7.3	Summary of Investigator CGI-I at End of Study/Early Withdrawal	ITT	Unique
13.1	Median Reduction in Seizure Burden and Percent of Spasm-Free Days	ITT	Unique
		ITT	Unique
Safety Section			
12.3.1	Summary of Exposure to Dronabinol Oral Solution by Treatment Group	Safety	Unique
12.2.1	Summary of Adverse Events by Treatment Group	Safety	Unique
12.2.2	Summary of Death and Serious Adverse Events by Treatment Group	Safety	Unique
12.2.4	Summary of Drug-Related Adverse Events by Treatment Group	Safety	Unique
12.6.1	Listing of Subjects Who Became Pregnant During the Study	Safety	Unique
12.6.2	Summary of Actual Values and Changes from Baseline in Clinical Chemistry Data by Treatment Group and Study Time	Safety	Unique
12.6.3	Summary of Actual Values and Changes from Baseline in Hematology Data by Study Time	Safety	Unique
12.7.1	Summary of Actual Values and Changes from Baseline in Vital Signs by Treatment Group and Study Time	Safety	Unique
12.8.1	Summary of Physical Examination Results		
12.9.1	Summary of ECG Data	Safety	Unique

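### The change from baseline in EEG spasm count compares a recording of at least 9 hours with one of 24 hours without scaling for time, which biases this descriptive summary towards worsening in infants who still have spasms

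*Protocol*

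**What the plan says.** Protocol 8.4.3 describes two recordings. The baseline is the screening EEG, given there as 9 hours, but section 3.1 makes 9 hours a floor: "minimum of a 9-hour video EEG that includes at least one full sleep-wake cycle during their Screening Visit". The comparison recording is fixed in length: "a 24-hour video EEG will be conducted from Day 14 to Day 15 of the Initial Treatment Period".

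The same section defines the measure ("For each video EEG, the number of spasms will be counted and the presence of hypsarrhythmia determined") and its summary ("Change from Baseline for each measure will be summarized by the median difference"). It leaves the details of these summaries to the SAP and bases all efficacy summaries on the ITT Population.

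The SAP keeps the 9-hour against 24-hour pairing (section 3.1), with the second EEG at Day 13 to 14 because it follows an earlier protocol version. Section 5.2.1 lists the EEG data as including "Presence of spasms (Y/N), Number of spasms" and the presence of hypsarrhythmia or epileptic encephalopathy; recording duration is not mentioned. Section 6.1 defines change from baseline, wherever it is calculated, as the post-baseline value minus the baseline value. The efficacy sections (10.1 to 10.7) give no rule for the change in EEG spasm count. Neither document mentions a rate per hour or a matched window.

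**The concern.** A count depends on how long one looks. Subtracting a count over about 9 hours from a count over 24 hours mixes any treatment effect with the difference in recording time. The shift is towards worsening for every infant whose screening EEG is shorter than 24 hours. Because 9 hours is only a minimum, the shift also differs between infants.

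At stake is the one planned summary of how far EEG spasm number changed, as opposed to whether spasms resolved. A reader of the study report would take a positive change as worsening and a small negative change as little benefit. For infants with residual spasms either reading could be wrong.

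**Working it through.** The documents state no figure on this point, so there is none to reproduce. The check is direct arithmetic.

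**Inputs**
- Baseline duration L: at least 9 hours, no upper limit (Protocol 3.1 and 8.4.3).
- Day 14 to 15 duration: 24 hours (Protocol 8.4.3).
- Change: post-baseline minus baseline (SAP 6.1).
- Baseline rate r spasms per hour, and ratio q of the later rate to the baseline rate. Both are assumptions, with the rate taken as constant over each recording. The percentages below do not depend on r.

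**Formula**
- Expected change in count = 24qr − Lr.
- As a share of the baseline count = 24q/L − 1.
- The change is zero at q = L/24, so the rate must fall by 1 − L/24 before the recorded change reaches zero.

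**Results**

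| Baseline EEG (L) | Rate unchanged (q = 1) | Rate halved (q = 0.5) | Fall needed to read as zero |
|---|---|---|---|
| 9 h | 24/9 − 1 = +167% | 12/9 − 1 = +33% | 1 − 9/24 = 62.5% |
| 10 h | +140% | +20% | 58.3% |
| 12 h | +100% | 0% | 50% |
| 16 h | +50% | −25% | 33.3% |
| 18 h | +33% | −33% | 25% |
| 24 h | 0% | −50% | 0% |

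**In counts.** Take r = 2 per hour and L = 9, for illustration. The baseline count is 18. An unchanged rate gives 48 (+30). A halved rate gives 24 (+6), whereas the change on a common time base is −1 per hour, or −24 per 24 hours.

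**Infants with no spasms at Day 14 to 15.** The change is 0 − Lr. In the same example it is −18, against −48 per 24 hours. The sign is right; the size is set by the baseline recording alone.

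**Chance for a single infant.** With Poisson counts, a 9-hour baseline and a halved rate, the probability that the count rises is 0.71 at 1 spasm per hour, 0.80 at 2, 0.92 at 5 and 0.98 at 10.

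**Effect on the arm medians.** Inclusion criterion 3 requires at least one cluster of 3 or more spasms on the screening EEG, so every infant who is spasm-free later changes by −3 or lower.
- Combined arm: at the 60% complete response assumed in Protocol 8.2, more than half the arm is spasm-free, so the median is negative whatever the recording lengths.
- Vigabatrin-alone arm: at the assumed 40%, the sign is open. If only complete responders are spasm-free, all other infants' rates halve, and every baseline EEG lasts 9 hours, the median infant reads +33% when the true change is −50%. If enough further infants lose their spasms but not hypsarrhythmia, the median is negative.

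**Between arms.** At equal r and L, the baseline term Lr is the same in both arms and cancels. In the example, −18 against +6 differs by −24, as does −48 against −24 on a 24-hour base.

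**The case against.** The strongest reply is that little depends on this summary. Change in EEG spasm count is in no primary or secondary endpoint list and has no test. Complete response and the two resolution endpoints ask whether spasms or hypsarrhythmia are absent on the 24-hour EEG, and need no subtraction. Both arms follow the same recording schedule, so neither is favoured by design if screening durations are balanced. All of this stands, and it limits the weight of the point.

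A second reply is that the EEG Charter, which is not among the documents, may define a scoring window or a rate. It may. But Protocol 6.1 gives the Charter the conduct and reading of the EEG, while section 8 and section 8.4.3 give analysis methods and these summaries to the SAP, which has no such rule and cites none.

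Third, SAP 5.2.1 says what the data include, so it need not be a full list. This is fair: the absence of duration there does not show that duration is not captured.

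Two stronger readings are tempting:
- *Improved infants may be misclassified as non-responders.* Table 2 words Non-Response as "No improvement or worsening of spasms/hypsarrythmia burden", which suggests a comparison of counts. But no text links the median-difference summary to response status, which a blinded central reader assigns. An infant who resolves neither spasms nor hypsarrhythmia is not a Complete or Partial Responder on counts or on rates, and those are the categories that 8.4.3 compares.
- *The SAP confirms the faulty comparison in a planned table.* SAP 14.2 lists "Median Reduction in Seizure Burden and Percent of Spasm-Free Days", but burden is undefined there. It is paired with a diary measure and may itself come from the diary.

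**Conclusion.** The point holds for the descriptive summary in Protocol 8.4.3. Followed as written, it biases the change in spasm count towards worsening, in both arms, among infants who still have spasms. At a 9-hour baseline the recorded change is +167% for an unchanged rate and +33% for a halved rate, and reaches zero only after a 62.5% fall. These are expected values under a constant rate; chance, or clustering by sleep and waking, can move an individual infant either way.

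A reader might infer that any infant whose rate has halved is recorded as worse. That is expected only for a screening EEG shorter than 12 hours, and the documents give no typical length. From 12 up to 24 hours the fall is understated, not reversed. A reader might also infer that the whole summary is reversed in sign; under the protocol's own 60% response assumption, the combined-arm median must be negative.

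The complete-response and resolution endpoints, and the Complete and Partial Response categories, are unaffected. This is a modest but real error in a prespecified efficacy summary.

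**What to change.** In Protocol 8.4.3 and SAP 5.2.1 and 6.1:
- Record the duration of each EEG, for example from start and stop times.
- Define the change from baseline on spasms per recorded hour. Alternatively, count both recordings over windows of equal length that include a full sleep-wake cycle.
- If the SAP 14.2 seizure-burden table uses EEG counts, apply the same rate there; if it uses the diary, say so.
- If the EEG Charter already sets a scaling rule, cite it in the SAP.

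SAP 9.7 already plans awake and sleep summaries of the baseline EEG. Reporting the rate separately for awake and sleep time would also lessen the reliance on a constant rate.

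On a common time base, a halved rate reads as a 50% fall at any screening duration. The cost is a few lines of wording and a duration field for each EEG. The documents do not say whether duration is already captured, but no extra patients, visits or procedures are needed. The SAP allows changes until it is finalised before database lock.

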8.1.2. Secondary Efficacy Endpoints

The secondary efficacy endpoints in the Initial Treatment Period of this study are:

- Percent of patients with resolution of infantile spasms as assessed by 24-hour video EEG from Day 14 to Day 15 (partial response).
- Percent of patients with resolution of hypsarrhythmia as assessed by 24-hour video EEG from Day 14 to Day 15 (partial response).
- Investigator impression of efficacy and tolerability of study drug (CGI-I) at Visit 6 (End of Study), or Early Withdrawal.
- Increase in the number of spasm-free days between Day 1 and Day 15 of the Initial Treatment Period, as determined by the seizure diary entries.
- For patients with a complete response during the Initial Treatment Period who continue: percent of patients who relapse during the Extended Treatment Period confirmed by video EEG following parent report of relapse, and time to relapse.

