8.2. Sample Size Determination

A total of 190 patients (130 and 60 patients in the two groups) will provide 80% power with a two-sided alpha of 0.05 to detect a difference in response rate, assuming the response with vigabatrin alone is 40% and the response with vigabatrin with Cannabidiol Oral Solution is 60%.

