### **10.7. Analysis of the Secondary Efficacy Endpoints**

#### **10.7.1. Secondary Efficacy Endpoints**

The secondary efficacy endpoints in this study are:

- Percent of patients with resolution of infantile spasms as assessed by 24-hour video-EEG from Day 13 to Day 14 (partial response).
- Percent of patients with resolution of hypsarrhythmia or pattern of epileptic encephalopathy as assessed by 24-hour video-EEG from Day 13 to Day 14 (partial response).
- Investigator impression of efficacy and tolerability of study drug (CGI-I) at Visit 5 (End of Study) or Early Withdrawal.
- Percent reduction in spasm-free days between the Initial Treatment Period (Days 1 to 14) and Screening Period (Days -14 to -1), as determined by the seizure diary entries.
- For patients with a complete response during the Initial Treatment Period who continue: percent of patients who relapse during the Extended Treatment Period confirmed by video-EEG following parent report of relapse, and time to relapse.
- For patients with partial response during the Initial Treatment Period who continue: percent of patients who achieve complete response during the Extended Treatment Period, confirmed by video-EEG following parent report, and time to complete response.

Percentage of patients with partial response will be compared for each endpoint between treatment groups using Fisher's exact test.

Parent impression of efficacy and tolerability as measured by Clinical Global Impression – Global Improvement Scale (CGI-I) will be summarized by visit and status of response (complete/partial and no response). Appropriate summary statistics will be displayed and the CGI-I will also be analyzed as a continuous scale:

- 1 = Very much improved
- 2 = Much improved
- 3 = Minimally improved
- 4 = No change

5 = Minimally worse

6 = Much worse

7 = Very much worse

Percent reduction in spasm-free days, will be calculated for each treatment group. Treatment groups will be compared using ANCOVA with baseline number of spasm-free days as a covariate.

Percent of Responders who relapse and Partial Responders who achieve complete response during the Extended Treatment Period will be compared between treatment groups using Fisher's exact test. Time to relapse and time to complete response will be visualized using Kaplan-Meier curves and compared with log-rank tests.

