### **10.7.2. Presentation of the Secondary Efficacy Results**

Percentage of Partial Responders at Day 14 will be summarized by treatment group and developmental stage, and the p-value presented. CGI-I results will be summarized as a frequency table and the mean and median score with the p-value. Percent change in spasm-free days, relapse rate, and rate of partial to complete response will be summarized by treatment group and p-value. Time to relapse and time to complete response will be presented by treatment group as Kaplan-Meier curves and p-value for log-rank test.

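### Protocol 8.4.3 and SAP 10.7.2, read literally, test the share of Partial Responders, a category that can shrink because patients become complete responders; the label on the listed EEG secondary endpoints leaves the numerator in conflict

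*Protocol*

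**What the plan says.** Protocol Table 2 (section 3.1) defines partial response as "Complete resolution of either spasms or hypsarrythmia confirmed by video EEG". Complete response requires both. Taken alone, 'either' could include both, but section 8.4.3 makes the categories exclusive: "Patients will be defined as having Complete Response, Partial Response, or Non-Response on Day 15". The same sentence then states the comparison: "the percentage of patients who achieve a Complete Response and Partial Responders in each treatment arm will be compared using a chi-square test".

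The Protocol's listed secondary endpoints (8.1.2) are resolution of each sign, with a label attached. The first reads "Percent of patients with resolution of infantile spasms as assessed by 24-hour video EEG from Day 14 to Day 15 (partial response"), and the hypsarrhythmia endpoint carries the same label. Section 8.4.3.2 tests these two resolutions by chi-square without the label.

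The SAP follows a similar pattern. Section 10.7.1 lists the two resolution endpoints with the label and adds: "Percentage of patients with partial response will be compared for each endpoint between treatment groups using Fisher's exact test". Section 10.7.2 says: "Percentage of Partial Responders at Day 14 will be summarized by treatment group and developmental stage, and the p-value presented". The hypotheses in SAP 10.3.2 concern absence of spasms and absence of the EEG pattern, and do not exclude complete responders.

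**The concern.** Complete response and non-response each have a clear direction. Partial response lies between them. Its share falls if partial responders become complete responders, and it also falls if they become non-responders. A two-sided test of that share cannot tell the two apart, so a significant difference with fewer partial responders on CBD may be produced by a drug that works.

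The label adds a practical problem. A programmer who applies Table 2 to an endpoint marked as partial response would drop complete responders from the numerator. One who follows SAP 10.3.2 would keep them. The two choices can point in opposite directions on the same data, and the documents should settle the choice before unblinding.

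**Working it through.** **Inputs from the documents.** Protocol 8.2: "A total of 190 patients (130 and 60 patients in the two groups) will provide 80% power with a two-sided alpha of 0.05", with complete response 40% on vigabatrin alone and 60% with CBD. Protocol 8.4.3: "For all inferential statistical tests, a 2-sided type I error rate of 0.05 will be used throughout". SAP 3.3: 120 versus 60, with 40% versus 62%. SAP 10.7.1 uses Fisher's exact test.

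**Assumed.** The documents give no partial-response rate. I take a placebo rate *c* and let a share *s* of the 20-point gain in complete response come from would-be partial responders, so the CBD rate is *c* − 20*s* points.

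**The plan's own figure first.** Pooled two-proportion power for 40% versus 60% with 60 and 130 patients is 73.3% (exact enumeration 73.0%), not 80%. The SAP design gives 80.3% by the same formula. The Protocol shortfall is a separate matter, and nothing below depends on it.

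**Method.** Exact enumeration: sum Bin(x; 60, p₀) × Bin(y; 130, p₁) over all (x, y) where the uncorrected chi-square test is significant at 0.05 and y/130 < x/60.

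Hand check at 30% versus 20%:
- pooled rate = (60 × 0.30 + 130 × 0.20)/190 = 44/190 = 0.2316
- null SE = √[0.2316 × 0.7684 × (1/60 + 1/130)] = 0.0658
- alternative SE = √(0.30 × 0.70/60 + 0.20 × 0.80/130) = 0.0688
- Φ[(0.10 − 1.96 × 0.0658)/0.0688] = Φ(−0.42) = 34%, which agrees with the exact 33.6%.

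**Partial Responder test, complete response 40% to 60%:**

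| Share of gain from partial responders | Placebo vs CBD partial response | Significant against CBD |
|---|---|---|
| none | 30% vs 30% | 2.6% |
| a quarter | 30% vs 25% | 11.3% |
| half | 30% vs 20% | 33.6% |
| all | 30% vs 10% | 92.1% |
| all | 35% vs 15% | 86.5% |
| all | 40% vs 20% | 81.9% |
| all | 50% vs 30% | 75.7% |

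At 30% versus 20% the observed share is lower on CBD in 92.8% of trials. Under the SAP design (60 versus 120, Fisher, complete response 40% to 62%), 30% versus 19% gives 35% and 30% versus 8% gives 95%.

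**One concrete trial.** Partial response 18/60 versus 13/130, complete response 24/60 versus 78/130, non-response 30% in both arms.
- Partial: χ² = 190 × (18 × 117 − 42 × 13)²/(60 × 130 × 31 × 159) = 12.03, p = 0.0005, fewer on CBD.
- Complete: χ² = 190 × (24 × 52 − 36 × 78)²/(60 × 130 × 102 × 88) = 6.60, p = 0.010, more on CBD.

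The same data give significance both ways.

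**Resolution endpoint counting complete responders.** Assume partial responders split evenly between the two signs. Spasm resolution on placebo is 40 + 15 = 55%. On CBD it is 60 + 5 = 65% (partial response 10%) or 60 + 10 = 70% (partial response 20%).
- 55% versus 65%: significant for CBD in 26%, against in 0.05%.
- 55% versus 70%: significant for CBD in 52%, against in 0.004%.

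**The case against.** The strongest reply is that the endpoints actually listed are not the exclusive category. Protocol 8.4.3.2, the SAP synopsis and the SAP 10.3.2 hypotheses all state resolution or absence of each sign, and complete responders satisfy both. In SAP 10.7.1, 'for each endpoint' fits two resolution endpoints and does not fit a single exclusive category. The table titles in SAP 14.2 pair partial response with absence of each sign. SAP 10.7.2 may be shorthand for the same two endpoints, since otherwise it offers no presentation of them. The sentence in Protocol 8.4.3 is general text and could mean complete and partial response combined, or one test across three categories.

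Most of this stands. A reader might infer that the first two secondary endpoints are themselves tested on the exclusive category, inside the multiplicity-controlled family. The documents do not support that: the correction applies to the listed secondary endpoints, and the exclusive Partial Responder share is not among them. Nor do both documents clearly prescribe this test; in the SAP the problem is mainly conflicting terminology.

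What does not go away is the literal text. Protocol 8.4.3 names Partial Responders straight after defining three categories. SAP 10.7.2 attaches a p-value to the same term, which the SAP uses for a separate group elsewhere: its Extended Treatment Period text names complete and partial responders separately, and SAP 10.3.2 tests whether partial responders later achieve complete response.

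**Conclusion.** The point holds in limited form. On its plain reading, Protocol 8.4.3 tests an intermediate category whose direction does not track benefit, and SAP 10.7.2 gives it a p-value. The label on the listed endpoints makes the numerator ambiguous.

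The size rests entirely on assumed partial-response rates. The chance of a significant result against CBD runs from about 3%, which is chance, when non-responders refill the category, to between 76% and 92% when the whole gain in complete response comes from partial responders. A reader might take the high figures as the expected behaviour of the trial; nothing in the documents says where the gain would come from. If the category is refilled, the test is uninformative rather than reversed. The primary endpoint is unaffected.

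**What to change.** - Protocol 8.4.3: delete the between-arm test of Partial Responders and keep the comparison of complete response.
- SAP 10.7.2: delete the p-value for Partial Responders.
- Protocol 8.1.2 and synopsis, and SAP synopsis, 10.3.2 and 10.7.1: delete the partial-response label from the two resolution endpoints, and align the table titles in SAP 14.2.
- SAP 10.7.1: reword the comparison as resolution of spasms (whatever the hypsarrhythmia result) and resolution of hypsarrhythmia (whatever the spasm result), with complete responders counted as successes in both. Protocol 8.4.3.2 and SAP 10.3.2 already imply this.
- Show complete, partial and non-response by arm descriptively only.

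The cost is wording in both documents. Data collection, sample size and trial conduct do not change.
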